14.6.2.2 Summary

The prior distribution of the parameters is summarized in [Table 14-27](#). The prior distribution of the DLT rates for provisional doses is summarized in [Table 14-28](#). Note that the posterior probability of excessive toxicity of the proposed starting dose for triple combination (LGX818+MEK162+LEE011) is 10.2% which satisfies EWOC criteria.

Table 14-27 Prior distribution of model parameters

Parameter	Means	Standard deviations	Correlation
$(\log(\alpha_1), \log(\beta_1))$	(-2.917, -1.820)	(0.986, 1.041)	0.233
$(\log(\alpha_2), \log(\beta_2))$	(-2.326, 1.564)	(1.107, 1.368)	-0.535
$(\log(\alpha_4), \log(\beta_4))$	(-2.066, -0.749)	(0.527, 0.563)	-0.116
η_{12}	0	1.528	NA
η_{14}	0.095	0.512	NA
η_{24}	0.020	0.392	NA
η_{124}	0.020	0.392	NA

Table 14-28 Summary of prior distribution of DLT rates for triple combo (LGX818+MEK162+LEE011) including current DLT data (up to Apr 16, 2013) from dual combo (LGX818+MEK162)

LEE011 (mg, 3 week on, 1 week)	Prior probabilities that Pr(DLT) is in interval			Mean	SD	Quantiles		
	[0.0, 0.16)	[0.16, 0.35)	[0.35, 1.00]			2.50%	50.00%	97.50%
MEK162 45mg BID, LGX818 450mg QD								
100	0.662	0.236	0.102	0.149	0.145	0.006	0.102	0.551
200	0.552	0.216	0.232	0.218	0.226	0.004	0.132	0.809
400	0.468	0.14	0.392	0.337	0.341	0.001	0.194	0.986
600	0.44	0.098	0.462	0.411	0.396	0	0.265	0.999
800	0.428	0.075	0.498	0.455	0.424	0	0.342	1
MEK162 45mg BID, LGX818 600mg QD								
100	0.632	0.204	0.164	0.174	0.195	0.002	0.097	0.72
200	0.543	0.169	0.288	0.253	0.281	0.001	0.129	0.926
400	0.472	0.106	0.423	0.373	0.381	0	0.202	0.998
600	0.447	0.073	0.481	0.439	0.423	0	0.291	1
800	0.434	0.056	0.51	0.476	0.443	0	0.39	1

14.6.2.3 Hypothetical dose escalation scenarios for triple combo (LGX818+MEK162+LEE011)

The BLRM model should make reasonable decisions during a study based on the observed toxicities particularly in early cohorts. After completion of a given cohort, the decision to dose escalate and actual dose chosen for the subsequent cohort will depend on the recommendation of the BLRM EWOC principle and medical review of all relevant data available up to date.

Table 14-29 shows some scenarios of dose levels recommended by the 10-parameter BLRM for the specified DLT observations.

Note that the next dose level is selected in concordance with the provisional dose levels of LGX818 and LEE011 specified in the protocol, to mimic possible on-study escalation steps. MEK162 is maintained at 45 mg BID. Since the main goal of the dose escalation is to escalate LEE011, LGX818 is fixed at 450mg in the table.

Table 14-29 Dose decisions recommended by BLRM

Scenario	LEE011 (mg, 3 week on, 1 week off)	Npat	Ntox	Next dose level LEE011 (mg, 3 week on, 1 week off)	P(Target)	P(over)	Median DLT rate
1	100	3	0	200	0.193	0.109	0.079
2	100	3	1	100	0.399	0.155	0.178
3	100	3	2	50	0.505	0.227	0.233
4	100	6	1	200	0.308	0.221	0.172
5	100 200	3 3	0 0	400	0.131	0.130	0.042
6	100 200	3 3	0 1	200	0.367	0.181	0.178
7	100 200	3 3	0 2	100	0.527	0.126	0.200
8	100 200	3 6	0 1	300	0.281	0.188	0.147
10	100 200	3 8	0 1	400	0.221	0.225	0.131
11	100 200 400	3 3 3	0 0 0	800	0.072	0.104	0.007
12	100 200 400	3 3 3	0 0 1	400	0.326	0.242	0.191
13	100 200 400	3 3 3	0 0 2	200	0.505	0.105	0.188
14	100 200 400	3 3 6	0 0 1	600	0.233	0.229	0.139

The BLRM model is performing reasonably for the hypothetical dose escalation scenarios. Within Table 14-29, it can be seen that the model leads to decisions that are in agreement with clinical sense. When no DLTs are observed in a cohort, the decision is to escalate the dose. When 1 DLT is observed in one cohort, the decision is to stay in the current dose level, or dose escalation depending on the size of the cohort. When more than 1 DLT is observed in one cohort, the decision is to dose de-escalation.

14.7.1 Definition of AE

AE Definition

- An AE is any untoward medical occurrence in a patient or clinical study patient, temporally associated with the use of study intervention, whether or not considered related to the study intervention.
- NOTE: An AE can therefore be any unfavorable and unintended sign (including an abnonnal laboratoly finding), symptom, or disease (new or exacerbated) temporally associated with the use of study intervention.

Events Meeting the AE Definition

- Any abnonnal laboratoly test results (hematology, clinical cheinistiy, or urinalysis) or other safety assessments (e.g., ECG, radiological scans, vital sign measurements), including those that worsen from baseline, considered clinically significant in the medical and scientific judgment of the investigator Any abnonnal laboratoly test results that meet any of the conditions below must be recorded as an AE:
- Is associated with accompanying symptoms;
- Requires additional diagnostic testing or medical/surgical intervention;
- Leads to a change in study dosing (outside of any protocol-specified dose adjustments) or discontinuation from the study, significant additional concomitant dmg ti·eatinent, or other therapy.
- Exacerbation of a chronic or intennittent preexisting condition including either an increase in frequency and/or intensity of the condition.
- New conditions detected or diagnosed after study ti·eatinent adininisti·ation even though it may have been present before the staii of the study.
- Signs, symptoms, or the clinical sequelae of a suspected dmg-dmg interaction.
- Signs, symptoms, or the clinical sequelae of a suspected overdose of either study intervention or a concoinant medication. Overdose per se will not be repolied as an AE/SAE unless it is an intentional overdose taken with possible suicidal/self-haiming intent. Such overdoses should be repolied regardless of sequelae.
- The signs, symptoms, and/or clinical sequelae resulting from lack of efficacy will be reoolied as an AE or SAE if they fulfill the definition of an AE or SAE and meet the

requirements as per [Section 8.1.8.1](#). Also, "lack of efficacy" or "failure of expected pharmacological action" does not constitute an AE or SAE.

Events	Meeting the AE Definition
--------	---------------------------

- | |
|--|
| 
• Any clinically significant abnormal laboratory findings or other abnormal safety assessments which are associated with the underlying disease, unless judged by the investigator to be more severe than expected for the patient's condition.• The disease/disorder being studied or expected progression, signs, or symptoms of the disease/disorder being studied, unless more severe than expected for the patient's condition.• Medical or surgical procedure (e.g., endoscopy, appendectomy): the condition that leads to the procedure is the AE.• Situations in which an untoward medical occurrence did not occur (social and/or convenience admission to a hospital).• Anticipated day-to-day fluctuations of preexisting disease(s) or condition(s) present or detected at the start of the study that do not worsen.• Worsening of signs and symptoms of the malignancy under study should be recorded as AEs in the appropriate section of the CRF. Disease progression assessed by measurement of malignant lesions on radiographs or other methods should not be reported as AEs. |
|--|

14.7.2 Definition of an SAE

If an event is not an AE per definition above, then it cannot be an SAE even if serious conditions are met (e.g., hospitalization for signs/symptoms of the disease under study, death due to progression of disease).

An SAE is defined as any untoward medical occurrence that, at any dose:
a. Results in death
b. Is life-threatening 
The term "life-threatening" in the definition of "serious" refers to an event in which the patient was at risk of death at the time of the event. It does not refer to an event that hypothetically might have caused death if it were more severe.

c. Requires inpatient hospitalization or prolongation of existing hospitalization 
In general, hospitalization signifies that the patient has been detained (usually involving at least an overnight stay) at the hospital or emergency ward for observation and/or treatment that would not have been appropriate in the physician's office or outpatient setting. Complications that occur during hospitalization are AEs. If a complication prolongs hospitalization or fulfills any other serious criteria, the event is serious. When in doubt as to whether "hospitalization" occurred or was necessary, the AE should be considered serious.
 
Hospitalization for elective treatment of a preexisting condition that did not worsen from baseline is not considered an AE.

d. Results in persistent disability/incapacity 
• The term disability means a substantial disruption of a person's ability to conduct normal life functions.• This definition is not intended to include experiences of relatively minor medical significance such as uncomplicated headache, nausea, vomiting, diarrhea, influenza, and accidental trauma (e.g., sprained ankle) which may interfere with or prevent everyday life functions but do not constitute a substantial disruption.
e. Is a congenital anomaly/birth defect
f. Other situations: 
• Medical or scientific judgment should be exercised in deciding whether SAE reporting is appropriate in other situations such as important medical events that may not be immediately life-threatening or result in death or hospitalization but may jeopardize the patient or may require medical or surgical intervention to prevent one of the other outcomes listed in the above definition. These events should usually be considered serious.• Examples of such events include invasive or malignant cancers, intensive treatment in an emergency room or at home for allergic bronchospasm, blood dyscrasias or

convulsions that do not result in hospitalization, or development of drug dependency or drug abuse.

- Progression of the malignancy under study (including signs and symptoms of progression) should not be reported as an SAE unless the outcome is fatal within the active collection period. Hospitalization due to signs and symptoms of disease progression should not be reported as an SAE. If the malignancy has a fatal outcome during the study or within the active collection period, then the event leading to death must be recorded as an AE on the CRF, and as an SAE with CTCAE Grade 5 (see the Assessment of Intensity section).

14.7.3 Recording/Reporting and Follow-up of AEs and/or SAEs

AE and SAE Recording/Reporting

The table below summarizes the requirements for recording adverse events on the CRF and for reporting serious adverse events on the CT SAE Report Form to Pfizer Safety. These requirements are delineated for 3 types of events: (1) SAEs; (2) nonserious adverse events (AEs); and (3) exposure to the study intervention under study during pregnancy or breastfeeding, and occupational exposure.

It should be noted that the CT SAE Report Form for reporting of SAE information is not the same as the AE page of the CRF. When the same data are collected, the forms must be completed in a consistent manner. AEs should be recorded using concise medical terminology and the same AE term should be used on both the CRF and the CT SAE Report Form for reporting of SAE information.

Safety Event	Recorded on the CRF	Reported on the CT SAE Report Form to Pfizer Safety Within 24 Hours of Awareness
SAE	All	All
Nonserious AE	All	None
Exposure to the study intervention under study during pregnancy or breastfeeding, and occupational exposure	All AEs/SAEs associated with exposure during pregnancy or breastfeeding Occupational exposure is not recorded.	All (and EDP supplemental form for EDP) Note: Include all SAEs associated with exposure during pregnancy or breastfeeding. Include all AEs/SAEs associated with occupational exposure.

- When an AE/SAE occurs, it is the responsibility of the investigator to review all documentation (e.g., hospital progress notes, laboratory reports, and diagnostic reports) related to the event.
- The investigator will then record all relevant AE/SAE information in the CRF.
- It is **not** acceptable for the investigator to send photocopies of the patient's medical records to Pfizer Safety in lieu of completion of the CT SAE Report Form/AE/SAE CRFpage.
- There may be instances when copies of medical records for certain cases are requested by Pfizer Safety. In this case, all patient identifiers, with the exception of the patient number, will be redacted on the copies of the medical records before submission to Pfizer Safety.
- The investigator will attempt to establish a diagnosis of the event based on signs, symptoms, and/or other clinical information. Whenever possible, the diagnosis (not the individual signs/symptoms) will be documented as the AE/SAE.

Assessment of Intensity

The investigator will make an assessment of intensity for each AE and SAE reported during the study and assign it to 1 of the following categories:

GRADE	Clinical Description of Severity
1	MILD adverse event
2	MODERATE adverse event
3	SEVERE adverse event
4	LIFE-THREATENING consequences; urgent intervention indicated
5	DEATH RELATED TO adverse event

Assessment of Causality

- The investigator is obligated to assess the relationship between study treatment and each occurrence of each AE/SAE.
- A "reasonable possibility" of a relationship conveys that there are facts, evidence, and/or arguments to suggest a causal relationship, rather than a relationship cannot be ruled out.
- The investigator will use clinical judgment to determine the relationship.

- Alternative causes, such as underlying disease(s), concomitant therapy, and other risk factors, as well as the temporal relationship of the event to study treatment administration, will be considered and investigated.
- The investigator will also consult the IB and/or product information, for marketed products, in his/her assessment.
- For each AE/SAE, the investigator **!!!!!!** document in the medical notes that he/she has reviewed the AE/SAE and has provided an assessment of causality.
- There may be situations in which an SAE has occurred, and the investigator has minimal information to include in the initial report to the sponsor. However, **it is very important that the investigator always make an assessment of causality for every event before the initial transmission of the SAE data to the sponsor.**
- The investigator may change his/her opinion of causality in light of follow-up information and send an SAE follow-up report with the updated causality assessment.
- The causality assessment is one of the criteria used when determining regulatory reporting requirements.
- If the investigator does not know whether or not the study treatment caused the event, then the event will be handled as "related to study treatment" for reporting purposes, as defined by the sponsor. In addition, if the investigator determines that an SAE is associated with study procedures, the investigator must record this causal relationship in the source documents and CRF, and report such an assessment in the dedicated section of the CT SAE Report Form and in accordance with the SAE reporting requirements.

Follow-up of AEs and SAEs

- The investigator is obligated to perform or arrange for the conduct of supplemental measurements and/or evaluations as medically indicated or as requested by the sponsor to elucidate the nature and/or causality of the AE or SAE as fully as possible. This may include additional laboratory tests or investigations, histopathological examinations, or consultation with other healthcare providers.
- New or updated information will be recorded in the originally completed CRF.
- The investigator will submit any updated SAE data to the sponsor within 24 hours of receipt of the information.

14.7.4 Reporting of SAEs

SAE Reporting to Pfizer Safety via CT SAE Report Form

- Facsimile transmission of the CT SAE Report Form is the preferred method to transmit this information to Pfizer Safety.
- In circumstances when the facsimile is not working, notification by telephone is acceptable with a copy of the CT SAE Report Form sent by overnight mail or computer service.
- Initial notification via telephone does not replace the need for the investigator to complete and sign the CT SAE Report Form pages within the designated reporting time frames.

14.8 Appendix 8: Liver Safety: Suggested Actions and Follow-up Assessments

Potential Cases of Drug-Induced Liver Injury

Humans exposed to a drug who show no sign of liver injury (as determined by elevations in transaminases) are termed "tolerators," while those who show transient liver injury, but adapt are termed "adaptors." In some patients, transaminase elevations are a harbinger of a more serious potential outcome. These patients fail to adapt and therefore are "susceptible" to progressive and serious liver injury, commonly referred to as DILI. Patients who experience a transaminase elevation above 3 x ULN should be monitored more frequently to determine if they are an "adaptor" or are "susceptible."

In the majority of DILI cases, elevations in AST and/or ALT precede TBili elevations (>2 x ULN) by several days or weeks. The increase in TBili typically occurs while AST/ALT is/are still elevated above 3 x ULN (ie, AST/ALT and TBili values will be elevated within the same laboratory sample). In rare instances, by the time TBili elevations are detected, AST/ALT values might have decreased. This occurrence is still regarded as a potential DILI. Therefore, abnormal elevations in either AST OR ALT in addition to TBili that meet the criteria outlined below are considered potential DILI (assessed per Hy's law criteria) cases and should always be considered important medical events, even before all other possible causes of liver injury have been excluded.

The threshold of laboratory abnormalities for a potential DILI case depends on the patient's individual baseline values and underlying conditions. Patients who present with the following laboratory abnormalities should be evaluated further as potential DILI (Hy's law) cases to definitively determine the etiology of the abnormal laboratory values:

- Patients with AST/ALT and TBili baseline values within the normal range who subsequently present with AST OR ALT values >3 x ULN AND a TBili value >2 x ULN with no evidence of hemolysis and an alkaline phosphatase value <2 x ULN or not available.

- For patients with baseline AST **OR** ALT **OR** TBili values above the ULN, the following threshold values are used in the definition mentioned above, as needed, depending on which values are above the ULN at baseline:
 - Preexisting AST or ALT baseline values above the normal range: AST or ALT values >2 times the baseline values AND $>3 \times \text{ULN}$; or $>8 \times \text{ULN}$ (whichever is smaller).
 - Preexisting values of TBili above the normal range: TBili level increased from baseline value by an amount of at least $1 \times \text{ULN}$ **or** if the value reaches $>3 \times \text{ULN}$ (whichever is smaller).

Rises in AST/ALT and TBili separated by more than a few weeks should be assessed individually based on clinical judgment; any case where uncertainty remains as to whether it represents a potential Hy's law case should be reviewed with the sponsor.

The patient should return to the investigator site and be evaluated as soon as possible, preferably within 48 hours from awareness of the abnormal results. This evaluation should include laboratory tests, detailed history, and physical assessment.

In addition to repeating measurements of AST and ALT and TBili for suspected cases of Hy's law, additional laboratory tests should include albumin, CK, direct and indirect bilirubin, GGT, PT/INR, total bile acids, and alkaline phosphatase. Consideration should also be given to drawing a separate tube of clotted blood and an anticoagulated tube of blood for further testing, as needed, for further contemporaneous analyses at the time of the recognized initial abnormalities to determine etiology.

A detailed history, including relevant information, such as review of ethanol, acetaminophen/paracetamol (either by itself or as a coformulated product in prescription or over-the-counter medications), recreational drug, supplement (herbal) use and consumption, family history, sexual history, travel history, history of contact with a jaundiced person, surgery, blood transfusion, history of liver or allergic disease, and potential occupational exposure to chemicals, should be collected. Further testing for acute hepatitis A, B, C, D, and E infection and liver imaging (e.g., biliary tract) and collection of serum samples for acetaminophen/paracetamol drug and/or protein adduct levels may be warranted.

All cases demonstrated on repeat testing as meeting the laboratory criteria of AST/ALT and TBili elevation defined above should be considered potential DILI (Hy's law) cases if no other reason for the LFT abnormalities has yet been found. **Such potential DILI (Hy's law) cases are to be reported as SAEs, irrespective of availability of all the results of the investigations performed to determine etiology of the LFT abnormalities.**

A potential DILI (Hy's law) case becomes a confirmed case only after all results of reasonable investigations have been received and have excluded an alternative etiology.

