Recommended Dose Modifications any time during a cycle of therapy

Investigations (Hepatic^{})**

Bilirubin: total bilirubin without ALT/AST increase above baseline value (confirmed 48-72hr later)^c

Grade 1 (> ULN – 1.5 x ULN)	Maintain dose level of LGX818 and MEK162 (and LEE011 in patients treated in triple-combination arm) with LFTs monitored bi-weekly.
Grade 2 (> 1.5 – 3.0 x ULN)	Interrupt dosing of LGX818 and MEK162 (and LEE011 in patients treated in triple-combination arm) until resolved to Grade ≤ 1, then: - If resolved in ≤ 21 days, then maintain dose level of LGX818 and MEK162 (and LEE011 in patients treated in triple-combination arm) - If resolved in > 21 days, then ↓ 1 dose level* of LGX818 and MEK162 (and LEE011 in patients treated in triple-combination arm) - If not resolved within 28 days, or if toxicity recurs, discontinue patient from all study drug treatment. Repeat liver enzyme and bilirubin tests twice weekly for 2 weeks after dose resumption.
Grade 3 (> 3.0 x ULN)	Interrupt dosing of LGX818 and MEK162 (and LEE011 in patients treated in triple-combination arm) until resolved to Grade ≤ 1, then ↓ 1 dose level - Repeat liver enzyme and bilirubin tests twice weekly for 2 weeks after dose resumption - If not resolved within 28 days, or if toxicity recurs, discontinue patient from all study drug treatment.
Grade 4 (> 10.0 x ULN)	Discontinue patient from study treatment.

Note: If Grade 3 or 4 hyperbilirubinemia is due to the indirect (non-conjugated) component only, and hemolysis as the etiology has been ruled out as per institutional guidelines (e.g., review of peripheral blood smear and haptoglobin determination), then ↓ 1 dose level* and continue treatment at the discretion of the investigator.

AST or ALT without bilirubin elevation > 2 ULN (confirmed 48-72hr later)^c

Grade 1	Maintain dose level of LGX818 and MEK162 (and LEE011 in patients treated in triple-combination arm) and monitor LFTs biweekly.
---------	--

Recommended Dose Modifications for (dual) LGX818 and MEK162 or (triple) LGX818 and MEK162 and LEE011 combination study treatment

Worst Toxicity CTCAE v4.03 Grade (unless otherwise specified)^a

Recommended Dose Modifications any time during a cycle of therapy

AST or ALT without bilirubin elevation > 2 ULN (confirmed 48-72hr later)^c (continued)

Grade 2

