Interrupt dosing of LGX818 and MEK162 (and LEE011 in patients treated in triple-combination arm) until resolved to Grade ≤ 1 (or Grade ≤ 2 in case of liver metastasis), then:
 - If resolved in ≤ 21 days, maintain dose level of LGX818 and MEK162 (and LEE011 for triple-combination arm).
 - If resolved in > 21 days, then ↓ 1 dose level* of LGX818 and MEK162 (and LEE011 for triple-combination arm).
 - If not resolved within 28 days, discontinue patient from all study drug treatment.
Repeat liver enzyme and bilirubin tests twice weekly for 2 weeks after dose resumption.

Grade 3 (> 3.0 x ULN)

Omit dose of LGX818 and MEK162 (and LEE011 in patients treated in triple-combination arm) until resolved to ≤ baseline grade, then ↓ 1 dose level of dose level of LGX818 and MEK162 (and LEE011 in patients treated in triple-combination arm). If not recovered to ≤ baseline grade within 28 days, discontinue patient from all study drug treatment.
Repeat liver enzyme and bilirubin tests twice weekly for 2 weeks after dose resumption. If toxicity recurs, discontinue patient from all study drug treatment.

Grade 4 (> 10.0 x ULN)

Discontinue patient from study drug treatment.

AST or ALT and Bilirubin^d

For patients with normal ALT and AST and total bilirubin at baseline: AST or ALT > 3.0 x ULN combined with total bilirubin > 2 x ULN without evidence of cholestasis^e

Discontinue patient from study drug treatment.

For patients with elevated AST or ALT or total bilirubin at baseline: baseline: (AST or ALT > 2 x baseline AND > 3.0 x ULN) OR (AST or ALT 8.0 x ULN) — whichever is lower — combined with (total bilirubin > 2 x baseline AND > 2.0 x ULN)

Discontinue patient from study drug treatment.

Recommended Dose Modifications for (dual) LGX818 and MEK162 or (triple) LGX818 and MEK162 and LEE011 combination study treatment

Worst Toxicity CTCAE v4.03 Grade (unless otherwise specified)^a

Recommended Dose Modifications any time during a cycle of therapy

Investigations (Metabolic)

Asymptomatic amylase and/or lipase elevation

Grade 1 (> ULN – 1.5 x ULN)	Maintain dose level of LGX818 and MEK162 (and LEE011 in patients treated in triple-combination arm) and initiate appropriate medical therapy and monitoring.

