^d All patients with ALT or AST >5.0x ULN and total bilirubin > 1.5x ULN in the absence of cholestasis must immediately be withdrawn from study treatment and every attempt should be made to carry out the **liver event follow-up assessments** as described below in [Section 6.3.3](#).
If combined elevations of AST or ALT and total bilirubin do not meet the defined thresholds, please follow the instructions for isolated elevation of total bilirubin and isolated elevation of AST/ALT, and take a conservative action based on the degree of the elevations (e.g. discontinue treatment at the situation when omit dose is needed for one parameter and discontinue treatment is required for another parameter). After all elevations resolve to the defined thresholds that allow treatment re-initiation, re-start the treatment either at the same dose or at one dose lower if meeting a criterion for dose reduction

^e “Cholestasis” defined as: ALP elevation (>2.0 x ULN and R value (ALT/ALP in x ULN) ,2.0) in patients without bone metastasis, or elevation of ALP liver function in patients with bone metastasis.

^f All values refer to the average of triplicate measurements.

^g Ophthalmic monitoring mandated for retinal event, posterior uveitis, RVO: further evaluation with specialized retinal imaging (e.g. ocular coherence tomography, angiography).

^h Except: 1) lymphopenia unless clinically significant, 2) occurrence of KA and/or cutaneous SCC, 3) alkaline phosphatase, 4) AEs not considered clinically significant like alopecia study drug-related fever, electrolyte abnormalities (including K, NA, Cl, HCO₃, Mg, Ca, PO₄).

* ↓ 1 dose level refers to: next lower previously tested dose level of LGX818 and LEE011 and the next lower dose level of MEK162 (please see [Table 6-1](#) and [Table 6-2](#)).

Recommended Dose Modifications for (dual) LGX818 and MEK162 or (triple) LGX818 and MEK162 and LEE011 combination study treatment

**Worst Toxicity CTCAE v4.03 Grade
(unless otherwise specified)^a**

Recommended Dose Modifications any time during a cycle of therapy

** Confounding factors and/or alternative causes for increased transaminases should be excluded before dose interruption/reduction. They include but are not limited to: concomitant medications, herbal preparations or dietary supplements, infection, hepato-biliary disorder or obstruction, new or progressive liver metastasis, and alcohol intake.

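### In a narrow band of raised-baseline bilirubin, Table 6-4 footnote d permits restart of a patient who meets the Appendix 8 potential Hy's law criteria, even when the evaluation excludes other causes

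*Protocol*

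**What the plan says.** **Appendix 8 (Section 14.8)** defines potential drug-induced liver injury by Hy's law. For raised baseline bilirubin the limit is: "Preexisting values of TBili above the normal range: TBili level increased from baseline value by an amount of at least" 1 x ULN, or a value above 3 x ULN, whichever is smaller. It is combined with ALT or AST above 3 x ULN (and above twice baseline if raised at baseline), ALP below 2 x ULN or not available, and no hemolysis. A case that repeat testing supports, with no other reason yet found, is reported as an SAE. It becomes confirmed when the investigations have excluded another etiology. Appendix 8 gives no dosing instruction.

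**Table 6-4 (Section 6.3.2)** governs dosing and does not refer to Appendix 8.

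- Combined row, normal baseline: permanent discontinuation for ALT or AST above 3 x ULN "combined with total bilirubin > 2 x ULN without evidence of cholestasis".
- Combined row, raised baseline: discontinuation for the transaminase limit "combined with (total bilirubin > 2 x baseline AND > 2.0 x ULN".
- Footnote d, withdrawal: patients with ALT or AST above 5 x ULN and bilirubin above 1.5 x ULN without cholestasis "must immediately be withdrawn from study treatment and every attempt should be made to carry out" the liver follow-up.
- Footnote d, below those limits: "please follow the instructions for isolated elevation of total bilirubin and isolated elevation of AST/ALT", taking the more conservative action of the two.
- Footnote d, restart: "After all elevations resolve to the defined thresholds that allow treatment re-initiation, re-start the treatment either at the same dose or at one dose lower".
- Isolated bilirubin row, Grade 2: interrupt until Grade 1 or better, then "If resolved in ≤ 21 days, then maintain dose level of LGX818 and MEK162" (and LEE011 in the triple combination).

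**The concern.** The reporting rule and the dosing rule use different bilirubin limits for the same patient. Between the two limits, a patient can be a potential Hy's law case, have every other cause excluded, and so count as confirmed under Appendix 8. The written dosing instruction still leads to restart once the laboratory values recover.

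The double-asterisk footnote to Table 6-4 does not help. It says "Confounding factors and/or alternative causes for increased transaminases should be excluded before dose interruption/reduction", but names no different action once those causes have been excluded.

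What is at stake is re-exposure of a patient with confirmed drug-induced liver injury. With normal baseline values, the same on-treatment results (ALT 4 and bilirubin 2.6 x ULN, no cholestasis) require permanent discontinuation. The hazard is not theoretical for these drugs: Section 1.2.2.2.1 reports a fatal acute liver failure, suspected as related, in the MEK162 phase II study. No planned analysis is affected.

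**Working it through.** All values are in multiples of ULN. The plan states no figure of its own for this gap, so the check compares its thresholds.

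**Inputs**

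- Baseline bilirubin b: raised means above 1.0; exclusion criterion 7 (Section 5.3) caps it at 1.5.
- Appendix 8 bilirubin limit: the smaller of b+1 and 3. For b up to 1.5, b+1 is at most 2.5, so the limit is b+1.
- Table 6-4 combined stop, raised baseline: above both 2b and 2.0. For b above 1 this is above 2b.

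**Bilirubin band.** Width = 2b - (b+1) = b - 1, which is positive for every b above 1.

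| b | Appendix 8 met from | Combined stop above | Width |
|---|---|---|---|
| 1.1 | 2.1 | 2.2 | 0.1 |
| 1.2 | 2.2 | 2.4 | 0.2 |
| 1.3 | 2.3 | 2.6 | 0.3 |
| 1.4 | 2.4 | 2.8 | 0.4 |
| 1.5 | 2.5 | 3.0 | 0.5 |

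Every value in the band lies above 2.0 and up to 3.0. As printed in the isolated bilirubin row (above 1.5 to 3.0), that is always Grade 2: interrupt, then resume. The recovery target, Grade 1 or better (up to 1.5), is the patient's own baseline grade.

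**Transaminase window.** With baseline ALT or AST equal to a, the lower limit is the larger of 3 and 2a, and the upper limit is 5, above which footnote d requires withdrawal. The window is 2.0 wide for a up to 1.5, 1.0 at a = 2.0, 0.2 at a = 2.4, and closed at a = 2.5.

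**Worked case.** Baseline ALT 0.8, bilirubin 1.4. On treatment ALT 4, bilirubin 2.6, ALP 1.0, no hemolysis or cholestasis.

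1. Appendix 8: ALT above 3, and bilirubin 2.6 is at or above 1.4 + 1 = 2.4. Met.
2. Combined stop: needs bilirubin above 2 x 1.4 = 2.8. Not met.
3. Footnote d withdrawal: needs ALT above 5. Not met.
4. Isolated rows: bilirubin Grade 2 means interrupt and resume. ALT 4 falls under the printed label Grade 3 (> 3.0 x ULN): omit, recover to baseline grade, resume one level lower.
5. Conservative action under footnote d: neither row requires discontinuation, so the stricter result is restart one dose level lower.

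Two variants mark the edges. With ALT 6, footnote d requires withdrawal. With bilirubin 2.9, the combined stop applies.

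**The case against.** The strongest reply is that the two rules serve different purposes. Appendix 8 triggers work-up and reporting, and Table 6-4 controls dosing. A reporting trigger may properly be more sensitive than a stopping rule, and adjusting for baseline is deliberate: 1.4 to 2.6 is a 1.9-fold rise (2.6 / 1.4), short of the stated doubling. That stands, and it is why the thresholds need not change. It does not explain why restart is independent of the cause found.

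The second reply is that safeguards exist, and they are substantial:

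- The bilirubin and AST/ALT rows require recovery within 28 days.
- Under Section 6.3.2, an interruption over 21 days means discontinuation unless there is objective clinical benefit, the investigator judges continuation to be in the patient's interest, and the sponsor has been consulted.
- Recurrence of the bilirubin elevation, or of the > 3.0 x ULN AST/ALT elevation, means discontinuation.
- Tests are repeated twice weekly for 2 weeks after restart.
- Section 6.3.3 recommends a full work-up for LEE011 patients.
- The SAE goes to the sponsor within 24 hours (Section 8.1.1.1).
- The investigator may stop treatment (Sections 6.1.5 and 7.1.4.1).

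These narrow the risk. None bars a first restart after recovery within 21 days, and the recurrence rules act only after re-exposure.

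Three stronger readings are tempting and not supported. A reader might infer that any raised-bilirubin patient who meets Appendix 8 can be restarted; above 2b, or with ALT or AST above 5 x ULN without cholestasis, stopping is already mandatory. A reader might infer that restart is compelled; Table 6-4 gives recommended modifications and leaves discretion. A reader might infer same-dose restart; that needs ALT 4 to be read as Grade 2, against the printed label, and disregards the conservative-action instruction.

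**Conclusion.** The gap is real, narrow and minor. It needs all of the following:

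- baseline bilirubin above 1.0 and up to 1.5 x ULN;
- on-treatment bilirubin from b+1 to 2b;
- ALT or AST above 3 (and above twice baseline if raised at baseline) and up to 5 x ULN;
- ALP below 2 x ULN, with no hemolysis or cholestasis;
- recovery within the time limits.

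Inside that band the text permits restart of a case that Appendix 8 would call confirmed, in practice one dose level lower under the printed AST/ALT label. The bilirubin band is at most 0.5 x ULN wide.

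Reach is at most the 10 patients on treatment at Amendment 10, whose summary of changes lists Appendix 8 as an addition. Enrollment was already closed (Section 14.10.1). How many of the 10 had raised baseline bilirubin is not stated, so the number affected may be zero.

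The conclusion rests on the grade limits as printed and on finding no other text that makes restart depend on cause.

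**What to change.** Add to Table 6-4, footnote d:

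> A patient who meets the Appendix 8 potential Hy's law criteria is not restarted under the isolated-elevation rows unless the Appendix 8 evaluation has established another cause; otherwise study treatment is permanently discontinued.

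All thresholds and the SAE reporting rule stay as they are, and a patient with another established cause can still resume.

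The cost is one sentence in a written amendment, with the approvals in Section 12.1. The downside is a longer interruption, or discontinuation, for the rare patient in this band.
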